# No delay for recovery from Grade ≥2 allowed ## Unless grade at baseline was Grade ≥2 and AE has resolved to baseline grade.

# Note: Grade 4 AEs fulfilling DLT criteria will always lead to BNT411 discontinuation.

# First occurrence of AE fulfilling DLT criteria Grade 3:

- As a first measure, administration of BNT411 needs to be withheld.
- Investigator must contact sponsor for thorough discussion in order to decide whether the patient should be withdrawn from BNT411 treatment or next dosing should be delayed.
- Administration of BNT411 can be delayed for up to 21 days (i.e. one cycle) unless otherwise approved by the sponsor's medical monitor. If the intensity resolves to Grade ≤1 or baseline within this period, re-treatment may be considered under the following circumstances:
  - Sponsor and investigator will discuss any safety concerns in order to decide whether the next dose of BNT411 should be administered at the same dose level or one dose level lower (DL-1). Intermediate dose levels defined in the protocol may also be considered. The sponsor may also consult the SRC.

# Second occurrence of an identical AE Grade 3 after re-exposure to BNT411:

- As a first measure, administration of BNT411 needs to be withheld.
- If re-treatment leads to an identical AE with the same intensity, the next administration of BNT411 can be delayed for up to 21 days unless otherwise approved by the sponsor's medical monitor. If the intensity of the AE resolves to Grade ≤1 or baseline within this period, re-treatment may be considered under the following conditions:
  - The next dose of BNT411 should be administered at one dose level lower (DL-1 or DL-2) than the dose level causing the recurrence of the AE. Intermediate dose levels defined in the protocol may be considered.

#### Third occurrence of an identical AE Grade >2 after re-exposure to BNT411:

- As a first measure, administration of BNT411 needs to be withheld.
- If re-treatment at a lower dose leads to a third identical AE with intensity Grade ≥2, the patient must permanently discontinue trial drug. No dose delay is allowed. However, if the AE is Grade ≤1 or baseline, re-treatment may be considered under the following condition:
  - The next dose of BNT411 should be administered at the same reduced dose level (DL-1 or DL-2).

#### Please note:

• Re-escalation of BNT411 dose is not allowed for patients who previously have been dose-reduced.

- BNT411 must be permanently discontinued if the patient experiences an AE fulfilling the DLT criteria (after the DLT period has ended for the dose escalation or during the expansion) that fails to resolve to Grade ≤1 within 21 days after the planned dosing date unless otherwise approved by the sponsor's medical monitor.
- BNT411 must be permanently discontinued if more than 2 dose reductions are required.
- BNT411 must be permanently discontinued in the case of a dose delay of more than 21 days due to toxicity possibly related to BNT411 unless otherwise approved by the sponsor's medical monitor.
- The investigators are encouraged to contact the sponsor in the case of any safety concerns that need thorough discussion and evaluation.

# 6.6.3.2 Handling of Adverse Events Fulfilling the DLT Criteria after the DLT Period has ended in Part 1B

AEs that fulfill the DLT criteria after the DLT period has ended in the dose-escalation phase of Part 1B of the trial (i.e. from Cycle 2 Day 1 and beyond) or during the expansion (i.e. from Cycle 1 Day 1 and beyond) should be handled as shown in Figure 6-2.

Please Note: Patients must complete the DLT monitoring period prior to implementing the dose modification criteria outlined in this section.

[figure not shown]

Figure 6-2: Handling of adverse events fulfilling the DLT criteria after the DLT-observation period has ended – Part 1B

DL, dose level

\*Dose delay: Next dose of BNT411 can maximally be delayed 21 days unless approved otherwise by the sponsor medical monitor.

# No delay for recovery from Grade ≥2 allowed

## Unless grade at baseline was Grade ≥2 and AE has resolved to baseline grade.

# Note: Grade 4 AEs fulfilling DLT criteria will always lead to BNT411 discontinuation.

# First occurrence of AE fulfilling DLT criteria Grade 3:

- As a first measure, administration of BNT411 needs to be withheld.
- Investigator must contact sponsor for thorough discussion in order to decide whether the patient should be withdrawn from BNT411 treatment or next dosing should be delayed.
- Administration of BNT411 can be delayed for up to 21 days (i.e. one cycle) unless otherwise approved by the sponsor's medical monitor. If the intensity resolves to Grade ≤1 or baseline within this period, re-treatment may be considered under the following circumstances:
  - Sponsor and investigator will discuss any safety concerns in order to decide whether the next dose of BNT411 should be administered at the same dose level or one dose level lower (DL-1). Intermediate dose levels defined in the protocol may also be considered. The sponsor may also consult the SRC.

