# 6 Trial Treatment

# 6.1 Trial Treatment(s) Administered

Trial treatment may refer to the following compounds, either:

- 1. BNT411, and/or
- 2. Atezolizumab, and/or
- 3. Carboplatin, and/or
- 4. Etoposide.

BNT411 is a highly potent and selective small molecule TLR7 agonist of the imidazoquinoline family being developed by BioNTech and is a new investigational agent to be tested clinically in this trial. In all countries participating in the trial, BNT411 is considered as investigational medicinal product (IMP).

Atezolizumab is a PD-L1 blocking antibody indicated for the treatment of patients with various cancer diagnoses at different stages. Atezolizumab was first approved by FDA on May 18, 2016 to treat urothelial carcinoma, and similar positive opinion by European Medicines Agency (EMA) followed in July 2017. Carboplatin is a platinum coordination compound and etoposide is a topoisomerase inhibitor. They are both cytotoxic agents used in various chemotherapy regimens to treat many cancer indications. On March 18, 2019, the FDA approved atezolizumab in combination with carboplatin and etoposide, for the first-line treatment of adult patients with ES-SCLC. Since then, it has become a standard-of-care treatment in the US. In October 2019, EMA issued similar positive opinion for the combination. For the purpose of this trial, in the USA and UK, atezolizumab, carboplatin and etoposide are considered as non-investigational medicinal products (NIMPs). However, the individual drugs are considered as IMPs in Spain and Germany at the request of the competent authorities due to their use in combination with BNT411.

Information relating to COVID-19 vaccinations including a risk-benefit assessment and guidance for vaccination during this clinical trial is provided in Sections 10.8 and 10.9.

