#### Immune-related AEs that are considered DLTs:

- Any Grade 4 irAEs regardless of duration.
- Grade 3 colitis that does not downgrade to Grade ≤2 within 3 days after onset of the event despite maximal supportive care including systemic corticosteroids or downgrade to Grade ≤1 or baseline within 14 days.
- Any Grade 3 or Grade 4 non-infectious pneumonitis regardless of duration.

- Any Grade 3 irAEs, excluding colitis and pneumonitis, that does not downgrade to Grade ≤2 within 3 days after onset of the event despite maximal supportive care including systemic corticosteroids or downgrade to Grade ≤1 or baseline within 14 days.
- Any Grade 2 pneumonitis that does not resolve to Grade ≤1 within 3 days of the initiation of maximal supportive care.
- Liver transaminase elevation higher than 8×ULN or total bilirubin higher than 3×ULN.
- Any other toxicity that is greater than baseline grade, is clinically significant and/or unacceptable, and is judged to be a DLT by the investigator and the sponsor.
- The definition excludes the following conditions:
  - o Grade ≤4 lymphopenia which is not considered clinically significant by the investigator.
  - o Grade 3 endocrinopathy that is managed with or without systemic corticosteroid therapy and/or hormone replacement therapy and the patient is asymptomatic.
  - ⊙ Grade 3 inflammatory reaction attributed to a local anti-tumor response (e.g. inflammatory reaction at sites of metastatic disease, lymph nodes) that resolves to Grade ≤1 within 3 weeks.
  - o Concurrent vitiligo or alopecia of any AE grade.

[figure not shown]

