# **6.6.4** Dose Modification for Specific Adverse Events

## 6.6.4.1 Immune-related Adverse Events (irAEs) – For Part 1B Only

Guidance for BNT411 dose modification and management of irAEs is provided in the Table 6-1 below. For Grade 1 irAEs, trial treatment should be continued with close monitoring. Corticosteroids taper should be initiated over the course of at least 4 to 6 weeks when the irAE improves to Grade ≤1. Permanent discontinuation of trial treatment is recommended with Grade 4 toxicities with the exception of endocrinopathies that have been controlled by hormone replacement. Trial treatment should also be permanently discontinued for any Grade 3 irAE that recurs and for any life-threatening irAE. For additional guidance on the recommended management of irAEs, please refer to the *Management of Immune-Related Adverse Events in Patients Treated with Immune Checkpoint Inhibitor Therapy: American Society of Clinical Oncology Practice Guideline* (Brahmer et al, 2018). Furthermore, guidelines for the monitoring and management of potential cytokine release syndrome (CRS) can be found in Attachment 12.1.

BioNTech SE BNT411-01 Version 6.0

Table 6-1: BNT411 Dose Modification and Management of irAEs

Immune-related AEs	Toxicity Grade (CTCAE v5.0)	Dose Modification	Guidance for Management of irAEs
Pneumonitis	Grade 1-2 Grade 3 or 4	1st occurrence If there is radiographic evidence of pneumonitis progression, hold treatment until there is evidence of improvement/ resolution to Grade 1 or less¹  2nd occurrence: Permanently discontinue  Permanently discontinue	Monitor for signs and symptoms of pneumonitis  Evaluate for pneumonitis with radiographic imaging  For Grade ≥2:  Consider initiation of corticosteroid treatment (initial dose of 1-2 mg/kg prednisone or equivalent followed by taper).  Corticosteroid taper should be initiated when the irAE improves to Grade ≤1
Colitis	Grade 2	Hold treatment until resolved to baseline 	Monitor for signs and symptoms of colitis. Consider
Contis			gastroenterology consultation and confirm diagnosis of colitis
Grade 3 Grade 4		Refer to Sections 6.6.3.1 and 6.6.3.2  Permanently discontinue	Consider administration of corticosteroids (initial dose of 1-2 mg/kg prednisone or equivalent) followed by taper Corticosteroid taper should be initiated when the irAE
		improves to Grade ≤1	

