T1DM or Hyperglycemia	Newly diagnosed T1DM or Grade 3-4 hyperglycemia	Refer to Sections 6.6.3.1 and 6.6.3.2	Monitor for hyperglycemia or other signs and symptoms of diabetes Consider endocrinology consultation Consider administration of insulin for type 1 diabetes Consider administration of anti-hyperglycemic medication in patients with hyperglycemia
Hypophysitis	Grade 2	Continue treatment at the discretion of the investigator	Monitor for signs and symptoms of hypophysitis. Consider endocrinology consultation Consider administration of corticosteroids and initiate hormonal replacements as clinically indicated. Corticosteroid taper should be initiated upon irAE improving to Grade ≤1
	Grade 3 or 4	Refer to Sections 6.6.3.1 and 6.6.3.2	
Hyperthyroidism	Grade 2	Continue treatment at the discretion of the investigator	Monitor for signs and symptoms of thyroid disorders Consider management with thionamides and beta-blockers as appropriate
	Grade 3-4	Refer to Sections 6.6.3.1 and 6.6.3.2	
	Grade 2	Continue treatment at the discretion of the investigator	Monitor for signs and symptoms of thyroid disorders. Consider endocrinology consultation
	Grade 3-4	Refer to Sections 6.6.3.1 and 6.6.3.2	Consider initiation of thyroid replacement hormones per standard of care

BioNTech SE BNT411-01 Version 6.0

Immune-related AEs	Toxicity Grade (CTCAE v5.0)	Dose Modification	Guidance for Management of irAEs	
Nephritis and Renal Dysfunction	Grade 1	Consider temporary hold pending consideration of baseline renal function and to confirm etiology 	Monitor for changes in creatinine levels  For Grade ≥2:  — If worsening or no improvement, consider	
	Grade 2	Hold treatment until resolved to baseline 	administration of corticosteroids (prednisone 1-2 mg/kg or equivalent) followed by taper  - Corticosteroid taper should be initiated upon irAE improving to Grade ≤1	
	Grade 3-4	Permanently discontinue		
Skin Adverse Reactions	Grade 1-2	Continue treatment at the discretion of the investigator	Based on the severity of the adverse reaction, consider administration of corticosteroids. Corticosteroid taper should be initiated upon irAE improving to Grade ≤1  For signs or symptoms of SJS or TEN, withhold and refer the patients for specialized care. If SJS or TEN is confirmed, permanently discontinue	
	Grade 3	Refer to Sections 6.6.3.1 and 6.6.3.2		
	Grade 4	Permanently discontinue		

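### Protocol 6.6.4.1 excepts hormone-controlled endocrinopathies from Grade 4 discontinuation, which does not fit the mandatory BNT411 stop in 6.6.3.2 (Part 1B, Cycle 2 onward)

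*Protocol*

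**What the plan says.** The relevant provisions are all in the Protocol.

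- **6.6.3.2** governs events in Part 1B that meet the DLT criteria after the DLT period, from Cycle 2 Day 1. It carries the note "Grade 4 AEs fulfilling DLT criteria will always lead to BNT411 discontinuation". Some other stops in that section can be waived by the sponsor's medical monitor; this one cannot.
- **6.6.2** sets the Part 1B DLT criteria. The immune-related list includes "Any Grade 4 irAEs regardless of duration". The only endocrine exclusion is "Grade 3 endocrinopathy that is managed with or without systemic corticosteroid therapy and/or hormone replacement therapy and the patient is asymptomatic".
- **6.6.4.1**, for Part 1B only, opens with "Guidance for BNT411 dose modification and management of irAEs is provided in the Table 6-1 below". It then says "Permanent discontinuation of trial treatment is recommended with Grade 4 toxicities with the exception of endocrinopathies that have been controlled by hormone replacement". The next sentence reads "Trial treatment should also be permanently discontinued for any Grade 3 irAE that recurs and for any life-threatening irAE".
- **Table 6-1** handles Grade 3-4 events in its four endocrine rows with "Refer to Sections 6.6.3.1 and 6.6.3.2".
- **6.1** introduces its definition with "Trial treatment may refer to the following compounds, either" and lists BNT411, atezolizumab, carboplatin and etoposide, joined by and/or.
- **6.6.5**, item 1 of the list for individual patients, stops BNT411 for an event that meets the DLT criteria. It gives no endocrine exception and no time limit.
- **6.6.7 to 6.6.9** leave dose changes of the other three drugs to their prescribing information and local standard of care.

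**The concern.** An endocrinopathy controlled by hormone replacement is the one kind of Grade 4 event that 6.6.4.1 takes out of its discontinuation advice. In 6.6.3.2 it is a mandatory stop like any other Grade 4 event that meets the DLT criteria. An investigator could reasonably take 6.6.4.1 as the more specific rule, because it deals with immune-related events and is introduced as BNT411 guidance. That investigator could then keep dosing BNT411 in a patient whom 6.6.3.2 requires to stop.

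The setting makes this worth settling. This is a first-in-human combination with atezolizumab, which the Protocol itself associates with immune-related events (2.3.2 and 6.6). Two sites could also treat the same kind of patient differently, and BNT411 discontinuation due to a TEAE is one of the primary endpoints in Section 3.

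**Working it through.** No arithmetic settles this point, so I applied each provision to one test case: a Part 1B patient in Cycle 2 or later with a Grade 4 immune-related endocrinopathy that is controlled by hormone replacement.

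**Step 1. Are the DLT criteria met?** Yes. Section 6.6.2 includes any Grade 4 immune-related event, and its endocrine exclusion is limited to asymptomatic Grade 3.

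**Step 2. What does each provision then say about BNT411?**

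| Provision | Outcome for the test case |
|---|---|
| 6.6.3.2, Grade 4 note | Must stop |
| 6.6.5, item 1 | Should stop; no endocrine exception |
| 6.6.4.1, sentence with the exception | Excepted from the recommended stop |
| 6.6.4.1, next sentence (life-threatening events) | Should stop; 10.3.3 describes Grade 4 as life-threatening |
| Table 6-1, endocrine rows | Refers to 6.6.3.1 and 6.6.3.2, hence stop |
| Table 6-1, row for all other events (an endocrinopathy without its own row) | Stop |

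The sentence with the exception is the only one that does not lead to a stop.

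**Step 3. Does any row of Table 6-1 give effect to the exception?** Five rows call for permanent discontinuation at Grade 4: pneumonitis, colitis, nephritis, skin, and all other events. Four refer to 6.6.3.1 and 6.6.3.2: type 1 diabetes or hyperglycemia, hypophysitis, hyperthyroidism, and the second thyroid row. That accounts for 5 + 4 = 9 rows, and none allows BNT411 to continue at Grade 4.

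**Step 4. Does the exception reach BNT411?** The definition in 6.1 can include it. The opening sentence of 6.6.4.1 and the title of Table 6-1 are about BNT411, and the other three drugs have their own sections. No sentence confines the exception to those drugs.

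**Step 5. Who is exposed?** Only Part 1B patients still on BNT411 from Cycle 2. Protocol 4.2 plans 6 to 30 DLT-evaluable patients in Part 1B. SAP Appendix 3 (Table 4) lists two Part 1B cohorts, 1.2 and 2.4 µg/kg. At three to six DLT-evaluable patients each (SAP Section 6), that is 2 × 3 = 6 to 2 × 6 = 12 patients before any backfilling. The documents give no rate for the event, so I do not quote a probability of a case.

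**The case against.** The strongest reply is that the plan already reaches the right answer. The exception qualifies a recommendation, and a site that stops BNT411 complies with every section. For the action on BNT411, 6.6.4.1 sends the reader to Table 6-1, whose endocrine rows lead back to the mandatory stop. A Grade 4 event would normally be an SAE, reported within 24 hours, and Section 8 sends immediate safety concerns to the sponsor to decide whether the patient continues. This stands, and it keeps the point small.

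A second reply is that the exception was meant for atezolizumab. The wording in 6.1 is permissive and does not make trial treatment mean BNT411 in every use. The Protocol also rates the risk of immune-related events from BNT411 alone as low. That intention is possible, but the text does not state it, and the framing of 6.6.4.1 as BNT411 guidance points the other way.

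Third, item 1 of 6.6.5 may be meant for Cycle 1, since item 2 deals with events after the DLT period. It sets no time limit, so I count it as supporting the stop but rest the conclusion on 6.6.3.2.

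A reader might infer that the Protocol tells sites to continue BNT411, or that two sections give opposite orders. The documents do not support that: one section is mandatory, and the other only withholds its recommendation for one case.

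**Conclusion.** The inconsistency is present in the current text and should be corrected, as a clarification. It is confined to Part 1B from Cycle 2 Day 1, to Grade 4 endocrinopathies controlled by hormone replacement, and to a site that follows the introductory text of 6.6.4.1 instead of Table 6-1 and 6.6.3.2. I expect such events to be rare, but that is a judgement without a documented rate.

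A reader might also infer that DLT counts, the MTD or dose escalation are affected. They are not. Cycle 1 DLTs are counted under 6.6.2, whatever is later done with BNT411. Cycle 1 dosing after a DLT has its own rule in 6.6, under which the sponsor may allow a patient to continue, possibly at a reduced dose.

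The conclusion assumes that trial treatment in 6.6.4.1 includes BNT411, which the section's framing supports. It also assumes that Figure 6-2, which I could not see, contains nothing that ranks the two rules. The Grade 4 note in 6.6.3.2 is explicit without it.

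**What to change.** Add one sentence to 6.6.4.1: the endocrinopathy exception does not apply to BNT411, for which 6.6.3.2 governs, while atezolizumab, carboplatin and etoposide follow 6.6.7 to 6.6.9. In the four endocrine rows of Table 6-1, separate Grade 4 from Grade 3 and enter permanent discontinuation for Grade 4.

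Do not simply delete the exception. Deletion would leave the Grade 4 recommendation applying to all trial treatment, including atezolizumab, against 6.6.7, which defers to the label.

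If the sponsor does intend the exception to cover BNT411, it has to be written into four other places: the Grade 4 note in 6.6.3.2, item 1 of the individual list in 6.6.5, the sentence on life-threatening events in 6.6.4.1, and the Grade 4 entry for all other events in Table 6-1.

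Either route is a protocol wording change with no effect on sample size, data collection or analysis. The clinical cost of the preferred route is that a few patients with a controlled hormone deficiency would stop BNT411.

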# Second occurrence of an identical AE Grade 3 after re-exposure to BNT411:

- As a first measure, administration of BNT411 needs to be withheld.
- If re-treatment leads to an identical AE with the same intensity, the next administration of BNT411 can be delayed for up to 21 days unless otherwise approved by the sponsor's medical monitor. If the intensity of the AE resolves to Grade ≤1 or baseline within this period, re-treatment may be considered under the following conditions:
  - The next dose of BNT411 should be administered at one dose level lower (DL-1 or DL-2) than the dose level causing the recurrence of the AE.
     Intermediate dose levels defined in the protocol may be considered.

# Third occurrence of an identical AE Grade ≥2 after re-exposure to BNT411:

- As a first measure, administration of BNT411 needs to be withheld.
- If re-treatment at a lower dose leads to a third identical AE with intensity Grade ≥2, the patient must permanently discontinue trial drug. No dose delay is allowed. However, if the AE is Grade ≤1 or baseline, re-treatment may be considered under the following condition:
  - Next dose of BNT411 should be administered at the same reduced dose level (DL-1 or DL-2).

#### Please note:

- Re-escalation of BNT411 dose is not allowed for patients who previously have been dose-reduced.
- BNT411 must be permanently discontinued if the patient experiences an AE fulfilling the DLT criteria (after the DLT period has ended for the dose escalation

- or during the expansion) that fails to resolve to Grade  $\leq 1$  within 21 days after the planned dosing date unless otherwise approved by the sponsor medical monitor.
- BNT411 must be permanently discontinued if more than 2 dose reductions are required.
- BNT411 must be permanently discontinued in the case of a dose delay of more than 21 days due to toxicity possibly related to BNT411 unless otherwise approved by the sponsor's medical monitor.
- The investigators are encouraged to contact the sponsor in the case of any safety concerns that need thorough discussion and evaluation.
- If the causal relationship of AE cannot be attributed to either BNT411, atezolizumab, carboplatin and etoposide, BNT411 should be discontinued; atezolizumab, carboplatin and etoposide should be dose modified as per the US Prescribing Information or the Summary of Product Characteristics.

